#### Figure 2: Identification of treated and untreated Time 0s

 $CKD = chronic kidney disease; D_x = diagnosis; T2D = type 2 diabetes.$ 

Note: The analytic cohort identified from these 2 hypothetical patients would consist of 1 observation in the exposure group and 5 observations in the comparator group. In individual 2, the first CKD diagnosis would not be an eligible untreated Time 0 because the patient had not yet met the T2D criterion.

#### 9.2.1.2. Selection criteria

Individuals must meet all the following inclusion criteria on or before Time 0 to be included in the cohort:

- Active registration or continuous enrolment for at least 365 days in the data source before Time 0 (days [-365, 0])
- No recorded use of finerenone before Time 0 (days [-all available, 0])
- Aged 18 years or older on Time 0
- Diagnosis of T2D at any time on or before Time 0 (days [-all available, 0])
- Evidence of CKD on or before Time 0 (days [-all available, 0]), identified by meeting any of the following criteria:
  - A diagnosis code indicating CKD stage 1, 2, 3, 4, or stage unspecified
  - Two UACR test results  $\geq$  30 mg/g separated by at least 90 days and no more than 540 days.
  - Two different eGFR test results  $\geq 15 \text{ mL/min}/1.73 \text{ m}^2 \text{ AND}$ < 90 mL/min/1.73 m^2 [17] separated by at least 90 days and no more than 540 days. If a reported eGFR test result is available in the data, it will be used as recorded to determine eligibility (as that was the eGFR value available to the prescribing clinician at the time of Time 0). If an eGFR value is not reported, but there is sufficient information to calculate the eGFR, it will be calculated using the creatinine-based 2021 CKD-EPI equation [18] (Section 9.3.1).

Individuals will be excluded if they meet any of the following exclusion criteria on or before Time 0:

- Type 1 diabetes (T1D) at any time on or before Time 0 (days [all available, 0]), as finerenone is not indicated for use in T1D
- Evidence of end-stage kidney disease (ESKD) at any time on or before Time 0 (days [all available, 0]) —as finerenone is not recommended to be initiated in individuals with ESKD or severely reduced eGFR—identified as any of the following criteria:
  - Two different eGFR test results < 15 mL/min/1.73 m^2 [17] separated by at least 90 days and no more than 540 days
  - Dependence on dialysis (at least 3 sessions over at least 90 days)
  - A diagnosis code indicating kidney failure or CKD stage 5 (International Classification of Diseases, 10th Revision, Clinical Modification [ICD-10-CM] code N18.5)
  - A diagnosis code indicating having a kidney transplant (ICD-10-CM code Z94.0)
- Diagnosis of kidney cancer at any time on or before Time 0 (days [-all available, 0]), as decreased renal function resulting from kidney cancer may differ in treatment response from diabetic CKD.
- A diagnosis of adrenal insufficiency (i.e., congenital adrenogenital disorders of enzyme deficiency, primary or secondary adrenocortical insufficiency, Addison's disease, pituitary neoplasm, or other pituitary disorder [19]) at any time on or before Time 0 (days [-all available, 0]), as finerenone is contraindicated in individuals with adrenal insufficiency [13]
- Evidence of hepatic impairment, including hepatic failure, fibrosis, cirrhosis, or chronic hepatitis, at any time on or before Time 0 (days [-all available, 0]), as treatment with finerenone is to be avoided in individuals with severe liver impairment [13]
- An eGFR measurement < 25 mL/min/1.73 m^2 on or in the 90 days before Time 0 (days [-90, 0]), as finerenone is not recommended to be initiated in individuals with eGFR < 25 mL/min/1.73 m^2 [13]
- Evidence of recent increased serum potassium or hyperkalaemia, as finerenone is not recommended for initiation in individuals with elevated serum potassium [13], identified as either of the following:
  - A serum potassium test result > 5.0 mEq/L on or in the 90 days before Time 0 (days [-90, 0])
  - A diagnosis code indicating hyperkalaemia on or in the 90 days before Time 0 (days [-90, 0])
- Use of a strong CYP3A4 inhibitor on or in the 183 days before Time 0 (days [-183, 0]), as finerenone is a CYP3A4 substrate and is contraindicated in users of strong CYP3A4 inhibitors [13]. Examples include the following [20,21]:
  - Cobicistat
  - Itraconazole

- Ketoconazole
- Posaconazole
- Ritonavir
- Telithromycin
- Troleandomycin
- Voriconazole
- Evidence of pregnancy measured on or in the 40 weeks before Time 0, as clinical practice guidelines discourage the use of finerenone during pregnancy [16]

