#### 9.2. Setting

#### 9.2.1. Study population and selection criteria

The source population for the study will consist of adults with CKD and T2D who are eligible for finerenone prescription after the approval of finerenone in the US. The study cohort will identify patients who initiate finerenone and a comparator group of individuals with CKD and T2D not using finerenone. All eligible adult individuals (aged  $\geq$  18 years) in the data source will be selected for the study cohort without sampling from the source population. There will be no restrictions of the study population based on sex, race, or ethnicity.

[figure not shown]
#### 9.2.1.1. Study entry and Time 0

The identification of potential Time 0s for the exposure and comparator groups is illustrated in Figure 2—a schematic of 2 hypothetical individuals with diagnoses of CKD and T2D, 1 of whom initiates finerenone.

The date of an individual's first observed prescription for finerenone during the cohort entry period will be Time 0 for the exposure group (i.e., the date a patient was initially prescribed finerenone). The selection criteria (Section 9.2.1.2) for the exposed group will be evaluated on Time 0. Only the first observed finerenone initiation date per person will be considered.

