The comparator group of patients with T2D and CKD untreated with finerenone will consist of all encounters during which an individual was recognised as having CKD and was eligible to be prescribed finerenone but was not. All calendar dates with an encounter with a recorded diagnosis of CKD will be considered as potential Time 0s. The selection criteria (Section 9.2.1.2) will be evaluated at every identified potential Time 0, and all Time 0s meeting the selection criteria will be included in the comparator group. Multiple comparator Time 0s per person may be eligible and selected (Figure 2), including dates for individuals who subsequently initiate finerenone (i.e., information on an individual's future prescription or dispensing for finerenone will not be used to define eligibility). Although this is difficult to confirm before conducting the analysis, the general assumption is that patients with CKD and T2D would visit a physician at least once per year. At each interaction, the physician could potentially recognise the patient as having CKD (i.e., record the diagnosis in the electronic health record [EHR]). When combining the above assumption with an estimated maximum study period of 3 years, we anticipate the number of potential Time 0s per individual in the comparator group to generally be less than 5.

T2D = type 2 diabetes.

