### 9.3. Variables

### 9.3.1. Measures of kidney function

Determining the level of kidney function (i.e., eGFR and CKD stage) is required at numerous points in this analysis to determine study eligibility and define baseline CKD stage. Kidney function may be determined either with eGFR measurements, recorded CKD diagnoses, or UACR measurements.

When required to be calculated from recorded serum creatinine values, eGFR will be calculated using the creatinine-based 2021 CKD-EPI equation (without including cystatin-C) [18,23-27]:

$$eGFR = 142 \times \min\left(\frac{Scr}{\kappa}, 1\right)^{a_1} \times \max\left(\frac{Scr}{\kappa}, 1\right)^{a_2} \times c^{Age} \times d$$

Where:

- $a_1 = -0.241$  for female individuals and -0.302 for male individuals
- $a_2 = -1.200$
- *c* = 0.9938
- d = 1.012 for female individuals and 1 for male individuals
- $\kappa = \text{is } 0.7$  for female individuals and 0.9 for male individuals
- min indicates the minimum of  $\frac{scr}{\kappa}$  and 1, and max indicates the maximum of  $\frac{scr}{\kappa}$  and 1.
- The coefficient  $a_1$  is used for levels of creatinine less than or equal to 0.9 mg/dL for male individuals and 0.7 mg/dL for female individuals.
- The coefficient  $a_2$  is used for levels of creatinine greater than 0.9 mg per decilitre for male individuals and 0.7 mg per decilitre for female individuals.

CKD stage at Time 0 (Section 9.3.3.3) will be defined based on either the most recent eGFR level or recorded diagnosis of CKD stage on or before Time 0. CKD stage based on eGFR categories (mL/min/ $1.73 \text{ m}^2$ ) or diagnosis coding will be defined as follows:

- Stage 1: eGFR  $\geq$  90, normal or high
- Stage 2: eGFR 60-89, mildly decreased
- Stage 3: eGFR 30-59, mildly to severely decreased
- Stage 4: eGFR 15-29, severely decreased
- Stage 5: eGFR < 15 or treatment with chronic dialysis or kidney transplant, ESKD
- Stage unspecified (for individuals with only stage-unspecified CKD diagnosis codes)

Albuminuria will be measured using the most recent UACR [28] value on or during the 365 days before Time 0, and selection criteria will include both eGFR and UACR-based entry definitions of kidney function (Section 9.2.1.2). For those individuals with UACR values

available, the extent of albuminuria will be categorised as follows (UACR mg/g is approximately equivalent to albumin excretion rate mg/d):

- A1: < 30, normal to mildly increased
- A2: 30-300, moderately increased

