This study will compare finerenone users with nonusers. While the study selection criteria are designed to ensure that all nonusers are eligible to be prescribed finerenone on all identified Time 0s, systematic differences in characteristics may be present between finerenone initiators and nonusers, resulting in unmeasured confounding (e.g., if finerenone users are generally at more advanced disease stages than nonusers, there may be a confounded estimate demonstrating an elevated outcome rate in treated individuals). This study uses a rich set of covariates, including demographic characteristics, comorbidities, and comedications, as well as proxies for healthcare-seeking behaviour and healthy lifestyle. The balance of measured characteristics will be evaluated, negative control outcomes will be evaluated to determine the potential impact of unmeasured confounding, and a sensitivity analysis will use restrictive inclusion criteria to create more similar treatment groups. However, the possibility of unmeasured confounding remains.

Comparisons of medication users with nonusers may be subject to selection bias if treated individuals must meet additional criteria (e.g., additional survival, healthcare interactions) to be included in the study beyond those of the comparator group criteria. For the comparator group in this study, all dates on which individuals had a recorded CKD diagnosis and were eligible for finerenone treatment will be included in the comparator group. This will include a large array of individuals with CKD at each timepoint their CKD was recognised and evaluated. However, if in practice, there are requirements for finerenone prescription that systematically require additional survival (e.g., a long evaluation period), selection bias may be present. This limitation also applies to analyses of the recommended titration schedule of finerenone. Individuals who do not follow the titration schedule will be censored, potentially introducing selection bias in follow-up. Inverse probability of censoring weights will be used to account for selection bias, but residual bias may remain if some key characteristics are not measured in the data.

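### Eligibility is worded alike for both arms but does not work alike: laboratory-only CKD admits essentially only initiators, and an untested patient passes the eGFR exclusion

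*Protocol*

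**What the plan says.** **When the criteria are applied.** Section 9.2.1.1 takes the exposed Time 0 as the first observed finerenone prescription, and "The selection criteria (Section 9.2.1.2) for the exposed group will be evaluated on Time 0". Comparator Time 0s are drawn only from dates with an encounter carrying a CKD diagnosis, and "The selection criteria (Section 9.2.1.2) will be evaluated at every identified potential Time 0". The abstract describes the comparator dates in the same way.

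**CKD evidence.** Section 9.2.1.2 requires "Evidence of CKD on or before Time 0 (days [-all available, 0]), identified by meeting any of the following criteria". It then lists three routes: a code for stage 1 to 4 or unspecified; two UACR results of at least 30 mg/g; or two eGFR results from 15 to below 90. For the two laboratory routes the results must lie 90 to 540 days apart.

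**Laboratory exclusions.** An eGFR below 25 excludes only if it was measured "on or in the 90 days before Time 0 (days [-90, 0]), as finerenone is not recommended to be initiated in individuals" below that level. Potassium has two triggers: "A serum potassium test result > 5.0 mEq/L on or in the 90 days before Time 0 (days [-90, 0"]), or "A diagnosis code indicating hyperkalaemia on or in the 90 days before Time 0 (days [-90, 0"]). The eGFR rule has no equivalent code trigger.

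**Staging and stated aim.** Under Section 9.3.1, CKD stage at Time 0 "will be defined based on either the most recent eGFR level or recorded diagnosis of CKD stage on or before Time 0", with no 90-day limit. Section 9.9 gives the purpose of the criteria: "While the study selection criteria are designed to ensure that all nonusers are eligible to be prescribed finerenone on all identified Time 0s". It then concedes that systematic differences may remain, and it promises a sensitivity analysis with restrictive inclusion criteria. Section 9.7.7 lists only the negative control analysis.

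**The concern.** In a user versus nonuser comparison, both arms should be drawn from patients who could have started treatment on that date and who were recognised as having the disease in the same way. Two features work against this.

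**Laboratory-only CKD.** A comparator date already carries a CKD code, so the UACR and eGFR routes add essentially nobody to that arm. They can add initiators. Such an initiator has no uncoded counterpart among the comparators.

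**No test counts as eligible.** A coded comparator with an eGFR of 18 at day -120 and nothing since passes the exclusion, and Section 9.3.1 may then stage that patient from that same value. An untested initiator passes too. If comparators are tested less often, which the protocol does not state, undetected ineligible patients would sit mainly among them. Section 9.9 itself says that untreated patients in a state that makes treatment unlikely are at higher risk of bad outcomes.

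At stake is a design-induced difference between the arms that could be of the same order as the random error in a study of this size.

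**Working it through.** **1. The plan's own figure.** Inputs from Section 9.5: RR 0.86, comparator risk p0 of 14.4% or 7.2%, ratio 10:1, 95% CI. With p1 = 0.86 × p0:

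SE(log RR) = √[(1−p1)/(n1·p1) + (1−p0)/(n0·p0)]; probability = Φ(−ln 0.86/SE − 1.96).

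- 30,000 records (2,727 exposed), 14.4%: 81.2%; pooled proportions 83.2%; Schoenfeld 80.8%.
- 60,000 records (5,455 exposed), 7.2%: 78.4%; pooled proportions 80.2%; Schoenfeld 80.8%.

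The stated 80% is reproduced to within the choice of formula. The present point does not depend on it.

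**2. Random error at the expected size.** Section 9.5 expects at least 20,000 initiators. With an assumed 200,000 comparators (10:1), SE(log RR) is 0.0196 at 14.4% and 0.0287 at 7.2%. Exp(±1.96·SE) is 0.962 to 1.039 and 0.945 to 1.058, so the unweighted half-width is about 4% to 6%.

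**3. How often a 90-day window is empty (illustration).** With Poisson testing, the share untested is exp(−rate × 90/365): 0.611 at 2 tests a year and 0.373 at 4. Both rates are assumptions. The formula also treats Time 0 as a random date, whereas comparator Time 0s are clinical encounters.

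**4. Undetected ineligible comparators.** Let f be the excess share of comparator records that are untested and truly ineligible, and k their risk relative to the rest. With a true RR of 1 and no weighting, apparent RR = 1/[1 + f(k−1)].

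- k = 2: 0.980, 0.952, 0.909 at f = 2%, 5%, 10%.
- k = 3: 0.962, 0.909, 0.833.
- k = 0.8: 1.004, 1.010, 1.020.

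**5. Laboratory-only initiators.** Let h be their share of the exposed and m their risk relative to coded initiators. Apparent RR = 1 + h(m−1).

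- m = 0.5: 0.975, 0.950, 0.900 at h = 5%, 10%, 20%.
- m = 0.7: 0.985, 0.970, 0.940.
- m = 1.2: 1.010, 1.020, 1.040.

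**6. Both together, one example.** f = 5%, k = 2, h = 5%, m = 0.7: 0.985/1.05 = 0.938.

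The documents give none of f, k, h or m. Taken one mechanism at a time, the range is 0.833 to 1.040, on both sides of 1.

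**7. What the covariates can and cannot do.** Section 9.3.4 lists CKD stage, albuminuria stage and the numbers of eGFR and potassium tests. An uncoded initiator with eGFR 60–89 is stage 2 under Section 9.3.1, as is a coded stage 2 comparator, so stage can balance while coding status does not. Stage 4 spans 15–29, so it does not separate 18 from 27 around the threshold of 25. A test count does not show whether an untested person was eligible.

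**The case against.** **Same rule in both arms.** A reader might infer that eligibility is tested differently by arm. It is not: one list is evaluated at Time 0 in both, and an untested initiator passes as an untested comparator does. Any asymmetry in the eGFR rule comes from unequal testing, for which the protocol gives no figure. This stands.

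**Direction.** A reader might also infer that both features favour finerenone. Untested does not mean ineligible, and untested patients may be healthier. The laboratory routes also admit patients with albuminuria or an eGFR as low as 15, so laboratory-only initiators need not be milder. The confounding example in Section 9.9 runs against finerenone. This stands; the sign changes with the inputs.

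**Overlap.** It would be too strong to say that laboratory-only initiators have no overlap with comparators. Codes for stages 1, 2 and unspecified qualify, so comparators with similar kidney function enter. What has no counterpart is coding status.

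**Size.** The figures above are crude, whereas the planned analysis is weighted on kidney severity and testing intensity, which should remove part of any effect. ESKD is already excluded over all lookback, so the untested ineligible are mainly those with eGFR 15–24. For f = 5%, that band would have to hold 0.05/0.611 = 8% or 0.05/0.373 = 13% of comparator records. No section supports such a share.

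**Flexibility already in the plan.** Section 9.7.2 allows eligibility to be altered if propensity scores are imbalanced, Section 9.9 admits residual differences, and Section 9.10.2 leaves missing-data detail to the SAP. None of these aligns the CKD evidence across arms, and a propensity score without coding status would not reveal the difference.

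**Conclusion.** The structural point holds on the text alone. The laboratory routes to CKD add essentially only initiators. The qualifier is needed because the comparator CKD code list is not shown; if it is wider than stages 1 to 4 and unspecified, a few comparators could qualify through laboratory values. The eGFR exclusion cannot ensure that every nonuser is eligible at every Time 0, because it requires no measurement and has no code back-up.

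The net direction and size are uncertain. The range of about 0.83 to 1.04 takes each mechanism alone, is unweighted, and rests on assumed shares and relative risks. A net distortion near 5% would be as large as the expected random error, but the documents neither establish nor exclude one. They do not support a claim of bias towards finerenone. The point is worth acting on because the asymmetry is built into the design, can be measured in the data, and is cheap to remove.

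**What to change.** Keep the stated thresholds, and change the following.

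1. **Section 9.2.1.2:** for the primary analysis, require a recorded CKD diagnosis code on or before Time 0 in both arms. Keep the laboratory-only route as a sensitivity analysis.
2. **Section 9.7.7:** list the restrictive-criteria sensitivity analysis promised in Section 9.9, and define it as requiring a measured eGFR and a measured potassium in the eligibility window in both arms. Optionally add a second with a longer eGFR lookback. That lookback is better kept out of the primary analysis, because it would exclude people on older values.
3. **Section 9.7.1:** report by arm the shares with no eGFR in the window, with no potassium in the window, and with laboratory-only CKD. These shares would show how much the point matters.
4. **Section 9.9:** say that eligibility is judged on recorded values and that an untested person counts as eligible.

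The cost is query wording. Initiators without a CKD code leave the primary analysis, so the statements in Sections 9.2.1 and 9.2.3 that all eligible individuals are included need adjusting. Untested records leave only the sensitivity analysis. One difference remains: comparators carry a code on the Time 0 date itself, initiators on or before it.

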### 9.2.1.3. Follow-up

Individuals will be followed-up from the day after Time 0 (i.e., day 1) until the first occurrence of 1 of the following:

- The date of an occurrence of the study outcome under evaluation (each outcome will be evaluated separately, and individuals may have different follow-up times for each outcome)
- Censoring at any of the following events:
  - End of the study period (i.e., end of available study data)
  - Loss to follow-up in the data source
  - Deviation from the treatment strategy defined on Time 0 for the primary analysis
    - Finerenone-exposed individuals discontinuing use of finerenone for reasons other than hyperkalaemia (pausing or discontinuing treatment for elevated serum potassium is consistent with treatment dose adjustment strategies [13]) or ESKD (discontinuing treatment for ESKD is consistent with treatment recommendations) [22]
    - Nonusers initiating finerenone

### 9.2.2. Study timeframe

The cohort entry period (the time period during which all Time 0s will be identified) will begin on 09 July 2021 (the date of FDA approval in the US) and will end at the latest available data in the data source at the time of analysis. Data from before 09 July 2021 will be used—and potentially back to 01 October 2015, as available—to define selection criteria, washout periods, and covariates.

### 9.2.3. Representativeness

The selection criteria for this study are designed to identify all individuals eligible for finerenone treatment according to the approved label [13] and medical society treatment recommendations [16]. Thus, the selection criteria for this real-world study differ from the more restrictive criteria used in pivotal randomised controlled trials [14,15]. In line with the approved label for finerenone in the US, this study includes a broader population than was included in the pivotal trials. Consequently, the results of this study will be representative of the on-label population in the US. This study will include all eligible individuals identified in the data source(s).

The initial data source used for this study will be the HealthVerity® Chronic Kidney Disease Masterset, which contains information on over 10 million unique patients, including those with commercial, Medicare Advantage, and Medicaid insurance plans.

### 9.3. Variables

### 9.3.1. Measures of kidney function

Determining the level of kidney function (i.e., eGFR and CKD stage) is required at numerous points in this analysis to determine study eligibility and define baseline CKD stage. Kidney function may be determined either with eGFR measurements, recorded CKD diagnoses, or UACR measurements.

When required to be calculated from recorded serum creatinine values, eGFR will be calculated using the creatinine-based 2021 CKD-EPI equation (without including cystatin-C) [18,23-27]:

$$eGFR = 142 \times \min\left(\frac{Scr}{\kappa}, 1\right)^{a_1} \times \max\left(\frac{Scr}{\kappa}, 1\right)^{a_2} \times c^{Age} \times d$$

Where:

- $a_1 = -0.241$  for female individuals and -0.302 for male individuals
- $a_2 = -1.200$
- *c* = 0.9938
- d = 1.012 for female individuals and 1 for male individuals
- $\kappa = \text{is } 0.7$  for female individuals and 0.9 for male individuals
- min indicates the minimum of  $\frac{scr}{\kappa}$  and 1, and max indicates the maximum of  $\frac{scr}{\kappa}$  and 1.
- The coefficient  $a_1$  is used for levels of creatinine less than or equal to 0.9 mg/dL for male individuals and 0.7 mg/dL for female individuals.
- The coefficient  $a_2$  is used for levels of creatinine greater than 0.9 mg per decilitre for male individuals and 0.7 mg per decilitre for female individuals.

CKD stage at Time 0 (Section 9.3.3.3) will be defined based on either the most recent eGFR level or recorded diagnosis of CKD stage on or before Time 0. CKD stage based on eGFR categories (mL/min/ $1.73 \text{ m}^2$ ) or diagnosis coding will be defined as follows:

- Stage 1: eGFR  $\geq$  90, normal or high
- Stage 2: eGFR 60-89, mildly decreased
- Stage 3: eGFR 30-59, mildly to severely decreased
- Stage 4: eGFR 15-29, severely decreased
- Stage 5: eGFR < 15 or treatment with chronic dialysis or kidney transplant, ESKD
- Stage unspecified (for individuals with only stage-unspecified CKD diagnosis codes)

Albuminuria will be measured using the most recent UACR [28] value on or during the 365 days before Time 0, and selection criteria will include both eGFR and UACR-based entry definitions of kidney function (Section 9.2.1.2). For those individuals with UACR values

available, the extent of albuminuria will be categorised as follows (UACR mg/g is approximately equivalent to albumin excretion rate mg/d):

- A1: < 30, normal to mildly increased
- A2: 30-300, moderately increased
- A3: > 300, severely increased
- Unknown, for individuals without baseline UACR values

The UACR categories will be identified if available, as they provide additional information regarding cardiovascular disease risk and kidney prognosis [5], but they will be defined as a separate variable from CKD stage; for CKD staging, only eGFR values or diagnosis codes will be used.

The most recent UACR value on or during the 365 days before Time 0 will be used as the baseline UACR value for the UACR-specific analysis set. Additional UACR laboratory values occurring during follow-up will be identified to define UACR-based outcomes.

Additionally, diagnoses of proteinuria and nephrotic syndrome will be identified. ICD-10-CM diagnosis codes for proteinuria do not indicate stage, and there may be considerable overlap between diagnosis-based measures and the UACR measurements for those with available laboratory values; however, diagnosis-based measures may be used in combination with laboratory test–based measures.

